Implementation of an ERAS program in patients undergoing thoracic surgery at a third-level university hospital. An ambispective cohort study.

(Short title: ERAS implementation in thoracic surgery)

31/12/2019

NCT ID not yet assigned

METHODS

Study design and participants

This study analyzes the implementation of an ERAS program in a thoracic service of a third level hospital (*Hospital Fundación Jiménez Díaz, Madrid, Spain*). To this end, we designed an ambispective cohort study, with a prospective arm of patients undergoing thoracic surgery within an ERAS program versus a retrospective arm of patients before the implementation of the protocol. Our centre's ethics committee approved our study before the start of patient recruitment, January 2018 Ref: EO071-18_FJD. This study followed the Strengthening the Reporting of Observational Studies in Epidemiology ([STROBE](#)) reporting guideline for cohort studies¹³.

After informed consent, we included patients consecutively since the implementation, except those who refused the inclusion in the study or were under 18 years old. We also asked for informed consent from the patients who were part of the retrospective cohort. For the calculation of the required sample size, we assumed that the ERAS program would result in a 25% reduction in the absolute risk of suffering a surgical complication. Since the surgical complication rate for our patients in 2016 was 40%, a type-I error of 5% and a power of 80% would require 47 patients per arm.

Procedures

We recruited 50 patients throughout 2018 and 2019 and compared them with data from the last 50 patients in 2016, the year in which we knew the surgical complication rate. We followed up each patient for 30 days after surgery through hospital and primary care medical records. Demographic and comorbidity data were collected from all patients, from which we calculated Charlson's comorbidity index¹⁴ for all patients.

We designed our centre's ERAS program through different measures during the preoperative, intraoperative and postoperative period. During the preoperative period, the patients and their families received comprehensive multidisciplinary information about the protocol, as well as their daily goals and expected discharge date. Also, a team

specialized in therapy against lung diseases taught patients pulmonary expansion exercises to be carried out until surgery was performed. Smoking cessation and nutritional screening of the patient were also part of this stage.

The patients underwent video-assisted thoracoscopic surgery (VATS), whenever possible, leaving a chest tube at the end of the surgery. All subjects received antibiotic and antithrombotic prophylaxis. Intraoperative management of patients was performed under general anaesthesia combined with regional techniques for pain control, avoiding the use of benzodiazepines and opioids. Those patients in whom thoracic epidural catheter was implemented during surgery continued its use through a patient-controlled analgesia system. Besides, a hot air system warmed the patients during surgery to maintain normothermia. Extubation was performed as soon as possible after the end of the surgery, and we encouraged early removal of the urinary catheter.

From the time of extubation, the patients began oral tolerance and respiratory physiotherapy exercises. Also, the patients were allowed to walk around early. The patients were discharged when they were free of complications, without severe pain, urinary catheter or chest tube.

Outcomes

The primary outcome was the number of patients with 30-day surgical complications. We defined air leakage, bleeding, infection, and reintervention as surgical complications. Secondary outcome included ERAS adherence, no-surgical complications, mortality, readmission, reintervention rates, pain (defined as any level of pain that prevents early ambulation) and hospital lenght of stay. To evaluate ERAS adherence, we defined seven items: VATS approach, regional analgesia, oral tolerance within 6 hours, urinary catheter removal within 24 hours, ambulation within 24 hours, respiratory physiotherapy within 24 hours and chest tube removal within 48 hours.

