## RESULTS

No patient declined inclusion in the study. The demographic characteristics and comorbidities of the patients are shown in Table 1. The two cohorts were not totally homogeneous, with a higher number of patients with hypertension in the standard cohort [26 (52%) vs ERAS 15 (30%),  $p = 0.03$ ] and chronic obstructive pulmonary disease [12 (24%) vs ERAS 4 (8%),  $p = 0.02$ ]. Although the number of patients with ASA class  $> 2$  was higher in the standard group [26 (52%) vs ERAS 15 (30%)], we found no difference between the cohorts in Charlson's comorbidity index. We included these three items, along with age and sex in the subsequent multivariate analyses.

Data on ERAS adherence and compliance for each of the protocol items are shown in Table 2. Adherence to the ERAS protocol was significantly higher in the prospective than in the retrospective cohort [Median: Standard 0.29 (0.14-0.43) vs ERAS 0.71 (0.57-0.82),  $p < 0.001$ ]. The VATS approach was greater in the ERAS group [29 (58%) vs Standard 11 (22%),  $p < 0.001$ ], and the number of patients who ambulated on the first postoperative day [40 (80%) vs Standard 0 (0%),  $p < 0.001$ ], but no difference was found in the use of regional analgesia. Also, the times to oral intake and removal of the urethral catheter were lower in the ERAS group [Median (h): Standard 24 (24-24) vs ERAS (6-7.5), and Standard 48 (24-48) vs ERAS 19 (6-24), respectively].

The primary and secondary results are shown in Table 3. We found no difference between the two groups in either surgical complications [Standard 18 (36%) vs 12 (24%),  $p = 0.19$ ], non-surgical complications [Standard 21 (42%) vs 12 (24%),  $p = 0.06$ ] or length of stay [Median (days): Standard 4 (3-6) vs 4 (3-5),  $p = 0.19$ ], and the ERAS group was significantly lower only in its readmission rate [Standard 15 (30%) vs 6 (12%),  $p = 0.03$ ]. No deaths were recorded in the ERAS group, compared to two deaths in the retrospective cohort.

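### The available text names no operation type or extent as a baseline variable, cohort comparison or covariate, so a case-mix difference could mask or mimic an ERAS effect on surgical complications

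*Protocol*

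**What the plan says.** **Who is included.** The Protocol (Study design and participants) describes "a prospective arm of patients undergoing thoracic surgery within an ERAS program" and states that "we included patients consecutively since the implementation, except those who refused the inclusion in the study or were under 18 years old". No procedure is required or excluded. Under Procedures, "We recruited 50 patients throughout 2018 and 2019 and compared them with data from the last 50 patients in 2016". The controls are not matched or restricted by operation.

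**What is recorded at baseline.** "Demographic and comorbidity data were collected from all patients", from which the Charlson index was derived (Protocol, Procedures). The SAP (RESULTS) describes the baseline table in the same terms: "The demographic characteristics and comorbidities of the patients are shown in Table 1".

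**Operative information.** VATS approach is recorded as an adherence item: "we defined seven items: VATS approach, regional analgesia, oral tolerance within 6 hours" and four others (Protocol, Outcomes). It is compared between cohorts in the SAP (RESULTS): 58% ERAS vs 22% standard. Epidural analgesia and intercostal block appear as model factors.

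**Primary outcome.** "We defined air leakage, bleeding, infection, and reintervention as surgical complications" (Protocol, Outcomes).

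**Analysis.** The SAP (Statistical analysis) compares the cohorts with Pearson or Wilcoxon rank-sum tests. The multivariable models take ERAS adherence as the exposure, whichever cohort the patient came from, and add clinical and demographic data. RESULTS then says of the covariates: "We included these three items, along with age and sex in the subsequent multivariate analyses".

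**The concern.** Air leakage, bleeding and reintervention depend heavily on what was operated on. A cohort with more lung resections would be expected to have more of these events than one with more minor procedures, whatever the perioperative program. Age, sex, Charlson index and ASA class describe the patient and say nothing about the operation.

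The cohort contrast on the primary outcome has no adjustment at all, because the multivariable models replace cohort membership with adherence. The cohorts are also separated in calendar time, and they already differ on measured factors: COPD 24% vs 8%, hypertension 52% vs 30%, ASA class above 2 52% vs 30%. Similarity on an untabulated factor cannot be taken for granted.

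The VATS difference shows the difficulty. It may reflect the program or a different set of operations, and without an operation class the two cannot be told apart. The adherence models share the gap: VATS and early chest tube removal are both part of the score, and the type of operation can influence both of them as well as air leak.

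At stake is whether the 12-point difference, or the finding of no significant difference, can be attributed to the program.

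**Working it through.** **1. The reported comparison.** Inputs from the SAP (RESULTS): 18/50 standard, 12/50 ERAS.

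- Pearson chi-square without correction = 100 × (18×38 − 32×12)² / (50×50×30×70) = 100 × 300² / 5,250,000 = 1.71, p = 0.190. This matches the stated 0.19.
- Risk difference = 0.36 − 0.24 = 0.12. SE = √(0.36×0.64/50 + 0.24×0.76/50) = √0.008256 = 0.0909. The 95% CI is 0.12 ± 1.96×0.0909, or −5.8 to 29.8 points.

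**2. Where operation type could enter.**

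| Step | What the available text names | Operation type or extent named? |
|---|---|---|
| Eligibility | Adults, thoracic surgery, consecutive | No |
| Baseline data | Demographics, comorbidity, Charlson, ASA class | No |
| Cohort comparison | Baseline items, adherence items including VATS, outcomes | No |
| Model covariates | Three baseline items, age, sex; analgesia techniques also reported | No |

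**3. Size of a case-mix effect.** Suppose operations fall into two classes with complication risks r_H (lung resection) and r_L (other), the same in both cohorts, and the program has no effect. If the share of resections is s_S in the standard cohort and s_E in the ERAS cohort, then

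difference = (s_S − s_E) × (r_H − r_L).

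The documents give none of these quantities, so the risk gap and the shift below are assumptions.

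| Assumed risk gap | Effect of a 20-point shift | As a share of the observed 12 points | Shift needed for all 12 points |
|---|---|---|---|
| 20 points | 0.20×0.20 = 4 points | 4/12 = 33% | 0.12/0.20 = 60 points |
| 30 points | 0.20×0.30 = 6 points | 6/12 = 50% | 0.12/0.30 = 40 points |
| 40 points | 0.20×0.40 = 8 points | 8/12 = 67% | 0.12/0.40 = 30 points |

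With 50 patients per cohort, a 20-point shift is 0.20×50 = 10 patients.

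**4. Direction.** If the ERAS cohort had fewer resections by 20 points, the mix-free difference would be 12−8 = 4 to 12−4 = 8 points. If it had more, it would be 12+4 = 16 to 12+8 = 20 points. The documents do not show which applies, or whether either does.

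**The case against.** Several points on the other side are sound.

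- **Data collected.** A reader might infer from the baseline sentence that only demographic and comorbidity data were collected. That is not so. The sentence explains the source of the Charlson index, and ASA class, VATS, analgesia technique and the timing items were clearly recorded. None of these identifies the operation, so the gap remains.
- **Absence.** A reader might conclude that operation type was never tabulated or adjusted for. The documents do not establish this. Tables 1 to 3, Figures 1 to 3 and part of the SAP file are not in the available text. The Statistical analysis section refers to unspecified clinical data, and the covariate sentence is incomplete, since analgesia techniques also appear in the models. The point can be made only for the available text.
- **Evidence of a shift.** A reader might infer that the 12-point difference is case mix. Nothing shows that. Both cohorts come from one service, ERAS inclusion was consecutive, and the interval from −5.8 to 29.8 points is compatible with chance alone. On the assumed gaps, explaining all 12 points needs a shift of 30 to 60 points, which is large.
- **Changing the primary test.** Results are already reported, so substituting a stratified test would be a post hoc change of the primary analysis. This objection stands, and the remedy respects it.

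The non-significant p-value does not answer the concern, because an imbalance can hide a benefit as well as create one.

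**Conclusion.** The concern holds as a gap in the plan as it can be read: unrestricted thoracic surgery, an operation-dependent primary outcome, an unadjusted cohort comparison, and no operation type or extent named as baseline variable, comparison or covariate. Case-mix confounding in either direction therefore cannot be excluded.

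The 4-to-8-point figure rests on an assumed 20-point shift, assumed risk gaps of 20 to 40 points, and a lung-resection-versus-other split that the documents do not themselves describe. It shows that a moderate imbalance would matter against 12 observed points. It does not estimate the bias that occurred. Confidence is moderate, because the tables and figures could not be read.

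**What to change.** 1. Extract a coarse operation class, lung resection versus other, from the hospital records of both cohorts and add it by cohort to Table 1. If the tables already hold it, state this in the text.
2. Keep the unadjusted Pearson comparison as planned. Report beside it a Mantel-Haenszel risk difference with 95% CI, stratified by operation class and labelled as a post hoc sensitivity analysis.
3. Add the same two-level variable to the logistic and Cox models, and list every covariate in the SAP.
4. If the classes are unbalanced or the stratified estimate differs materially from 12 points, qualify the primary conclusion. If they are balanced, one table row largely settles the matter.

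**Cost.** One field from 100 records, a few sentences in the SAP, some loss of precision, and one more degree of freedom. There are 18 + 12 = 30 primary events, and the surgical complication model already carries at least six terms (adherence, three items, age, sex), so a finer classification is not affordable. The analysis remains post hoc and must be reported as such.

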## Statistical analysis

We analyzed outcomes depending on whether the patient belonged to the ERAS program or the retrospective standard cohort. The discrete and continuous variables were described as number and percentage and median (interquartile range [IQR]) and their differences analyzed using the Pearson test or the Wilcoxon rank-sum tests. Subsequently, according to the adherence rate to ERAS items (regardless of whether the patients belonged to the ERAS or the retrospective standard cohort), We performed a multivariate logistic analysis to study the association of complication rates, readmission or pain with ERAS adherence, clinical and demographic data, presenting the results in forest plots as odds ratio with 95% confidence interval. Similarly, we used Cox regression for multivariate analysis of length of stay, presenting the results in forest plot as hazard ratio with 95% confidence interval. To avoid errors by multiple comparisons, we calculated the respective q-value for each p-value to maintain a false discovery rate below 5%. We considered comparisons in which p-value and q-value were below .05 as being statistically significant.

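### Pain is defined by failure to walk early while walking within 24 hours counts towards ERAS adherence, so the adherence–pain odds ratio is partly definitional if 'early' means 24 hours or longer

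*Protocol*

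**What the plan says.** The Protocol (Outcomes) lists pain as a secondary outcome, "pain (defined as any level of pain that prevents early ambulation". It builds the adherence score from seven items, two of which are "ambulation within 24 hours, respiratory physiotherapy within 24 hours". The Procedures section also uses the word 'early' for walking, again without hours: "Also, the patients were allowed to walk around early".

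The SAP (Statistical analysis) specifies a multivariable logistic model for the "association of complication rates, readmission or pain with ERAS adherence" together with clinical and demographic data. Patients enter it "regardless of whether the patients belonged to the ERAS or the retrospective standard cohort". On covariates, the RESULTS section says "We included these three items, along with age and sex in the subsequent multivariate analyses", and it also reports estimates for epidural analgesia and intercostal block. No cohort term is named, though the forest plots are not shown.

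RESULTS gives an adherence–pain OR of 0.01 (0.00, 0.28), p = 0.01. For the comparison by cohort it says that "the ERAS group was significantly lower only in its readmission rate".

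**The concern.** An exposure should not contain part of the outcome's definition. Here the pain outcome requires that the patient did not walk early, and the score gives credit for walking within 24 hours. If the two time limits coincide, or the limit for 'early' is longer, a patient with pain loses one adherence point whatever care was delivered. The regression then shows adherence as protective even when the other six items have no relation to pain.

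This matters because the statement that adherence goes with less pain appears to rest on this model alone. On the natural reading of RESULTS (Table 3 is not shown), pain did not differ significantly between the cohorts. The score is also closely tied to cohort: median 0.29 versus 0.71, and first-day walking 0/50 versus 40/50. A pooled model without a cohort term can therefore also pick up any cohort difference in pain.

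**Working it through.** **1. The reported figure.** The OR of 0.01 needs patient-level data and cannot be reproduced, but it is internally consistent. With SE = (ln 0.28 − ln OR)/1.96 and z = ln OR/SE, unrounded ORs from 0.0051 to 0.0149 give p from 0.010 to 0.005, in line with the printed p = 0.01. The OR spans the whole 0–1 score. One item is 1/7 of the scale, so it corresponds to 0.01^(1/7) = 0.52 per item.

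**2. The logic.** Let L be the limit meant by 'early'.
- L ≥ 24 h: pain means no walking by L, hence none by 24 h, so the item fails. Conversely, a patient who meets the item cannot have pain.
- L < 24 h: a patient can be kept from walking by L and still walk by 24 h, so the overlap is partial.

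The 24-hour item is the only limit that Outcomes attaches to walking. If first-day walking in RESULTS is the same as the 24-hour item (an assumption), L ≥ 24 h fixes pain at zero in 40 of 50 ERAS patients and in none of the 50 standard patients.

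**3. Possible size.** The simulations use 50 patients per cohort, walkers fixed at 0/50 and 40/50, and ERAS pain only among the 10 non-walkers. The other six items are unrelated to pain within cohort: VATS 22% versus 58% (RESULTS), regional analgesia 60% in both (assumed), and the remaining four set to give median adherence 0.28 versus 0.72. Each setting has 4,000 data sets, kept only if Pearson's test of pain by cohort gave p ≥ 0.05, to match RESULTS. The pain rates are assumed.

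| Setting | Seven-item OR (median) | Runs with p < 0.05 | Six-item OR |
|---|---|---|---|
| (1) Pain equally common in both cohorts, 5–20% | 0.36–0.44 | 1–11% | 0.98–1.06 |
| (2) Pain in 10–20% of non-walkers only | 0.12–0.13 | 7–24% | 0.22–0.26 |

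In (1) the whole departure from 1 comes from the shared item. In (2) most of it is cohort mixing: dropping the item leaves 0.22–0.26, and adding a cohort term to the six-item score brings it to 0.94–1.05. Expected pain counts in (2) are 5 versus 1 at 10% (p = 0.09) and 10 versus 2 at 20% (p = 0.014). Higher rates rarely agree with RESULTS (7% of runs kept at 30%, 0.1% at 50%).

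**4. Overlap against no overlap, at fixed pain counts without covariates.**

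| Pain, standard vs ERAS | Overlap forced: seven-item OR (p < 0.05) | No forced overlap: seven-item OR (p < 0.05) |
|---|---|---|
| 8 vs 8 | 0.36 | 1.03 |
| 10 vs 4 | 0.11 (42%) | 0.22 (13%) |
| 14 vs 7 | 0.12 (58%) | 0.29 (15%) |

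**5. With covariates.** These runs added age, sex, hypertension, COPD, ASA class above 2, and epidural and intercostal indicators, all unrelated to pain. ASA class was taken as the third covariate item, and the analgesia split is assumed. Equal counts from 3 vs 3 to 10 vs 10 gave seven-item ORs of 0.28–0.40 and six-item ORs of 0.99–1.36. Unequal but non-significant counts from 8 vs 3 to 18 vs 10 gave 0.08–0.09 and 0.19–0.29. Non-converged fits were excluded; only 43% converged at 3 vs 3, and 79–100% elsewhere.

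**6. Shorter limit.** If half of the ERAS patients with pain still walked by 24 h (8 vs 8 and 10 vs 10), the seven-item OR is about 0.7.

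**7. Against the reported value.** An OR of 0.015 or less with p of 0.015 or less occurred in at most 2.2% of kept runs in step 3, and in 3–8% of the unequal-count runs in step 5.

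**The case against.** The strongest reply is that the mechanism is conditional and small. Nothing in the documents ties 'early' to the 24-hour item. No standard patient walked on the first day, so the item is constant in that cohort and only the 40/10 split among ERAS patients can carry the overlap. Equal pain at 20% needs 10 ERAS events, that is, every ERAS non-walker held back by pain, which is an extreme case. Per item, an OR of 0.36–0.44 is only 0.86–0.89 (seventh root), against 0.52 for the reported value. The larger simulated effects are mostly cohort mixing, and whether a cohort term was fitted cannot be confirmed without the forest plots. Finally, the SAP already speaks only of association.

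Most of this stands as a limit on size. The condition is real, the pain counts are unknown, and the simulations seldom reach 0.01. Simulations that make the other six items equally common in both cohorts give stronger effects, but they contradict the reported adherence medians and are not relied on here.

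It does not remove the point. For any limit of 24 hours or longer the overlap follows from the definitions, whatever the data. The available text neither drops the item for the pain model nor offers a sensitivity analysis. Calling the result an association does not tell the reader that part of it is built in.

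**Conclusion.** The concern holds, with medium confidence. If 'early' means 24 hours or longer, the pooled adherence–pain OR is partly definitional and biased towards protection; with a shorter limit the overlap is partial. Under assumed pain rates and no true effect, the overlap alone moves the OR from about 1 to roughly 0.3–0.4. Where pain is also commoner in the standard cohort, overlap and cohort mixing together give roughly 0.1. These figures show possible size and do not estimate the actual bias. They rest on treating first-day walking as the 24-hour item, on assumed rates for most items, and on pain not differing significantly by cohort. The consequence is confined to one secondary outcome in one model, so this is a change that should be made but does not touch the study's main comparison.

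**What to change.** - State in the outcome definition the time limit that was meant by 'early'.
- Fit the pain model on the six-item score that omits walking.
- Report that model with a cohort term, or stratified by cohort, as a sensitivity analysis, because dropping the item alone leaves cohort mixing in place.
- If the seven-item OR is kept, describe it as an association that is partly definitional.

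The cost is one sentence in the SAP and a re-run on data already collected. In the simulations, dropping the item changed the standard error of the adherence coefficient by 4% or less. The cohort term raised it by about 41–43% and removes much of the adherence contrast, which is why it belongs in a sensitivity analysis. It may also not be estimable if ERAS pain events are few: in setting (2) at 10%, 13–15% of kept runs had no ERAS pain event. Reporting pain counts by cohort next to the model would let readers judge this.

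### Pain counts only when it prevents early walking, and first-day walking was 40/50 in ERAS and 0/50 in the standard cohort, so the pain outcome is not comparable between cohorts

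*Protocol*

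**What the plan says.** The Protocol (Outcomes) lists among the secondary outcomes "pain (defined as any level of pain that prevents early ambulation". It gives no intensity threshold, time window or assessor, and no rule for separating pain from other reasons for not walking.

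Early walking also appears in the description of the ERAS program (Procedures): "Also, the patients were allowed to walk around early". Three of the seven adherence items are "ambulation within 24 hours, respiratory physiotherapy within 24 hours and chest tube removal within 48 hours".

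On the cohorts and data source, Procedures states "We recruited 50 patients throughout 2018 and 2019 and compared them with data from the last 50 patients in 2016" and "We followed up each patient for 30 days after surgery through hospital and primary care medical records".

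The SAP (Statistical analysis) fits a multivariable logistic model "to study the association of complication rates, readmission or pain with ERAS adherence, clinical and demographic data", with patients pooled "regardless of whether the patients belonged to the ERAS or the retrospective standard cohort". The Results report, as higher in ERAS, "the number of patients who ambulated on the first postoperative day [40 (80%) vs Standard 0 (0" (percent). For pain, they report an odds ratio of 0.01 (0.00, 0.28) for adherence and 0.16 (0.03, 0.86) for thoracic epidural analgesia.

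**The concern.** The definition makes a pain event depend on not walking early. A patient who walked on the first day cannot be an event, whatever the pain; a patient who did not walk can be, at any level of pain. First-day walking differed almost completely between the cohorts, so the pool of patients who could be scored differed too. In the 2016 cohort nobody walked on the first day. Not walking therefore carries no information there about who had limiting pain, and each patient's status depends on the reason assigned from the records.

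At stake are the ERAS-versus-standard pain comparison and the two pooled pain odds ratios. Because the measurement error is tied to cohort, and cohort to adherence, a low adherence odds ratio for pain could partly reflect who walked rather than who hurt. The primary outcome is not affected.

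**Working it through.** **Inputs, all from the SAP (Results) unless noted.** First-day walking: ERAS 40/50, standard 0/50. Median adherence: 0.71 ERAS, 0.29 standard. Definition of pain and the 24-hour adherence item: Protocol (Outcomes). The documents give no design figure for pain, and the pain counts per cohort are in a table not shown.

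**Step 1. Who can be scored.** Assumption A: *early* means the first postoperative day. The pain definition gives no window; the 24-hour adherence item supports this reading.
- ERAS: 50 − 40 = 10 non-walkers, so pain is at most 10/50 (20%).
- Standard: 50 − 0 = 50 non-walkers, so the definition as worded leaves all 50 eligible.
- Exact 95% limits for first-day walking: 0/50 has upper limit 1 − 0.025^(1/50) = 7.1%; 40/50 gives 66% to 90%. Chance does not explain the gap.

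**Step 2. What the definition alone could produce.** Assumption B, for illustration: the same share f of non-walkers is coded as pain in each cohort. Counts are 50f (standard) and 10f (ERAS), a five-fold ratio of rates at any f. Odds ratio = [ERAS events × standard non-events] / [ERAS non-events × standard events]; p is the uncorrected Pearson test.
- f = 0.1: 5 vs 1; OR = (1 × 45)/(49 × 5) = 0.18; p = 0.09.
- f = 0.2: 10 vs 2; OR = (2 × 40)/(48 × 10) = 0.17; p = 0.014.
- f = 0.5: 25 vs 5; OR = (5 × 25)/(45 × 25) = 0.11; p < 0.001.

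**Step 3. What the reported results allow.** The Results say that ERAS was significantly lower only for readmission, and that no significant p-value was lost after the q-value step. If the unseen table includes pain, its p-value was therefore not below 0.05 in favour of ERAS. To bound the standard count, use z = difference / √[p̄(1 − p̄)(2/50)], where p̄ is the pooled proportion.
- Check against reported figures: surgical complications 18 vs 12, p̄ = 0.30, z = 0.12/0.0917 = 1.31, p = 0.19; readmission 15 vs 6, p̄ = 0.21, z = 0.18/0.0815 = 2.21, p = 0.03. Both match.
- With ERAS at its ceiling of 10: standard 18 gives p̄ = 0.28, z = 0.16/0.0898 = 1.78, p = 0.075; standard 19 gives p̄ = 0.29, z = 0.18/0.0908 = 1.98, p = 0.047. So standard pain was at most 18/50 (36%).
- With fewer ERAS events the cap is lower: at 5 it is 12/50.

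The f = 0.2 and f = 0.5 lines in Step 2 are therefore incompatible with the reported results on the same condition; the f = 0.1 line is compatible. Step 2 shows the mechanism and does not estimate the bias.

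**Step 4. Path into the models.** The adherence model pools the cohorts, and cohort is not among the adjustment variables named in the Results. The path to the adherence odds ratio is direct. The path to the epidural odds ratio is less so, because the Results report no cohort difference in regional analgesia, but that estimate uses the same outcome.

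**The case against.** The strongest case on the other side is that much of the damage is hypothetical. A reader might infer that standard-cohort pain could lie anywhere from near 0% to near 100%. The documents do not support that range. The upper end conflicts with the cap of 18/50, if the results table includes pain. The lower end is hard to square with a strongly protective adherence odds ratio when adherence was much lower in the standard cohort, though it is not strictly excluded.

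A reader might also infer that walking was not offered in 2016, or that ERAS patients had an observed attempt at walking while 2016 patients had only a chart reviewer's guess. Neither is stated. No text describes mobilisation practice in 2016, the Protocol says only that ERAS patients were allowed to walk early, and follow-up of every patient was through medical records. The 2016 records may have given the reason for not walking.

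These objections stand as limits on size and wording. They do not remove the unequal ceilings, which follow from the definition and the reported walking counts under Assumption A alone. Nor do they supply the missing rule for coding a non-walker.

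The point is also distinct from the fact that walking is one of the adherence items. Removing that item from the score would end the overlap, but pain would still be defined by walking and would still differ in meaning between cohorts.

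**Conclusion.** The concern holds for this secondary outcome and should be corrected before the pain results are used. Under the first-day reading of *early*, the definition makes 10 of 50 ERAS patients and 50 of 50 standard patients eligible to be scored, and in 2016 non-walking cannot by itself separate pain from other reasons for staying in bed. The pain outcome is not comparable between cohorts, and the error is tied to adherence in the pooled model. Its size and direction cannot be computed without the pain counts and the coding rule used; a different window for *early* would change both the ERAS ceiling and the cap of about 18/50 on standard-cohort pain. That the pain benefit is wholly an artefact is more than the documents show. Confidence is medium, because the window and the content of the 2016 records are undocumented.

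**What to change.** Redefine pain without reference to walking, using one item charted in both periods and abstracted identically: for example, a recorded pain score at a fixed postoperative time, or use of rescue analgesia, provided it is present in both sets of records. State the time window and the rule for missing entries. Rerun the between-cohort comparison and the pooled pain models, and report pain counts by cohort.

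If no common item exists, withdraw the between-cohort comparison and the pooled pain odds ratios as evidence of an effect. Report pain descriptively in ERAS only, with no multivariable model: under the existing definition at most about 10 events are available, too few for adherence plus the clinical and demographic covariates.

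The cost is re-abstraction of one item from 100 charts already reviewed or, failing that, loss of the inference on pain. Whether a suitable item was charted in 2016 is not known from the documents and should be checked first.
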